Study Title: A cluster randomized trial of a home-based intervention to increase uptake of postpartum contraceptives and its effect on short-interval pregnancy rates in a postpartum population of rural Guatemalan women

Principal Investigator: [name]

COMIRB No: 17-1314

Version: v30-Aug-2017

Summary: This study will involve a home-based intervention to increase uptake of contraception, especially the contraceptive implant, Jadelle®, in a postpartum population in the SW Trifinio region and document how increased uptake affects short-interval pregnancy rates. All contraceptives involved are already in common use in the population.

Problem: Adolescent pregnancy, high fertility rates, and high unmet need for contraception are a significant health sector problem for Guatemala, a Central American country, and are the public health problems of interest in this study [1]. According to the Guttmacher Institute, 11% of Guatemalan females are adolescents (age 15 – 19), 30% report having their sexual debut within this age range, and 22% of them have been married [2]. This study will focus on a sub-population (women age 15 – 35) of women from the rural Southwest (SW) Trifinio region of Guatemala who, according to a needs assessment and several program evaluation studies of the population, are particularly burdened by high fertility rates, high unmet need for contraception, and adolescent pregnancy [1]. The average birth spacing interval in this population is unknown [1]. Four percent of patients currently opt for Jadelle® as their birth-spacing method of choice, and the reported pregnancy rate in this group is unknown [1].

Significance and Use of Results: The previously mentioned research details the experience of North American populations living in a high-income country with access to healthcare resources. The objective of this research proposal is to study how improving access and delivery of contraception postpartum, by providing it in the home setting, can increase postpartum contraceptive uptake and reduce repeat pregnancy among a high-risk Central American rural population of women. No studies currently exist in the literature on interventions to increase postpartum contraceptive use in Guatemala. Information gleaned from this study will be used to learn more about the study population and subsequently perform additional studies aimed at increasing postpartum contraceptive use.

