This study will first address the question of whether provision of contraceptives in the home setting can increase uptake, especially of the postpartum implant Jadelle® in the population of interest. Second, it will observe whether or not the continuation rates and success seen with implant use in Northern American populations can be replicated in a Central American population. Third, the study will observe how acceptable the device is to the study population as

well as how manageable it is to supply and administer such devices in a rural, low-resource setting. And fourth, the intervention should increase knowledge regarding the effect of implant placement on short-interval pregnancy rates. As LARC implants are already widely used in HIC settings with, according to the WHO, minimal risk and significant benefit, we believe the importance of the knowledge gained in relation to the risk/benefit ratio favors performing the study intervention.

Background: Repeat short-interval pregnancies (< 12 months) are more likely to be complicated by preterm birth, stillbirth, maternal reliance on public assistance, termination of maternal education, and high subsequent parity [3]. A large proportion of attributable risk for major perinatal morbidity and mortality is related to short-interval pregnancy in the North American population [3]. While it is likely that there are similar attributable risks in other populations, there have been limited studies.

One method of preventing short-interval pregnancy is to encourage contraceptive use in the postpartum setting. Long-acting reversible contraceptive (LARC) methods provide effective contraception for an extended period without requiring user action; LARC generally includes intrauterine devices (IUD) and implants [4]. LARC, and in particular implants, have been shown to be highly effective in preventing rapid repeat pregnancy (< 12 months) [3].

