Different methodologies have been used to try and increase uptake of contraceptives in the postpartum setting. One study looked at the provision of contraceptives in the home, and found that clients had less days not covered by effective contraceptive use during the 90 days following a first birth [5]. The authors suggested that home dispensing of hormonal contraceptives may improve women's postpartum contraceptive use and should be explored as an intervention in communities where contraceptives are not easily accessible [5]. This study design did not include offering LARC in the home.

A research group from the Department of Obstetrics and Gynecology at the University of Colorado wanted to observe the actual clinical impact that such LARC devices might have on repeat pregnancy and contraceptive continuation rates among adolescents [3]. They conducted a prospective observational study of immediate postpartum implant insertion and found a 2.6% pregnancy rate one year post-placement, compared to an 18.6% pregnancy rate among the control group [3]. Their research shows that high continuation rates of postpartum LARC can translate into reduced immediate postpartum pregnancy rates. Downstream benefits of using LARC in this population also appeared to include a 2-percentage point decrease in preterm birth, which was an unexpected but highly beneficial outcome [3].

This study combines the two prior aforementioned study in a new population; it desires to look at home-based provision of contraceptive care, including LARC in the form of the progesterone-only implant called Jadelle®, and observing how this reduction of a barrier to access increasing uptake of all contraceptives, including abstinence. The hypotheses are:

Hypothesis 1: Offering routinely available contraceptives in a home setting can increase incidence of contraceptive initiation in a postpartum rural Guatemalan population.

Hypothesis 2: Increased use of long-acting reversible contraceptives placed in the home setting in a rural, postpartum Guatemalan population will decrease short-interval pregnancy rates.

Research Objectives: This study has the following objectives:

Objective 1: Increase uptake of routinely offered contraceptives in the postpartum setting by providing them to women at their home-based postpartum visit.

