Based on previously collected data, we expect that during our study timeframe around 260 women will meet eligibility criteria over the course of one year. The clusters will be randomly assigned by a biostatistician. This study, with 200 women enrolled (100 from intervention clusters and 100 from control clusters) will be powered to detect a change in Jadelle uptake rates from 3% to 15% at 85% power and 5% significance, with an intra class correlation of 2%.

[figure not shown]
Group	Proportion Positive	N Per Group	Standard Error	95% Lower	95% Upper
Population 1	0.03	100			
Population 2	0.15	100			
Rate Difference	-0.12	200	0.04	-0.20	-0.04

Alpha= 0.050, Tails= 2, Power = 0.848

Power computation: Normal approximation (unweighted mean p)
Precision computation: Log method

Phase II: Phase two of the study are six month and one-year follow-up visits that occur as part of routine care. Patients are immediately enrolled on delivery into Ninos Sanos, the early childhood health and development program offered through the CHD. Women and infants are seen monthly as part of the program, including routine visits at six and twelve months. At these sessions, mothers will be subject to a questionnaire regarding their contraceptive satisfaction and continuation habits, as well as whether or not they became pregnant since their delivery. This frequent and routine contact will ensure that patients are easily located for performing the follow-up questionnaire, but also will have no problem contacting study personnel if they have issues with their contraception or to report adverse events. We will also hold a focus group (interviews and surveys) for providers regarding their comfort and satisfaction with provision of care in the home setting before the study begins and after enrollment is complete.

Study Flow Diagram:

Study Visits: Patients who participate in the Community Health Services program through the CHD receive routine antepartum counseling on postpartum contraception in their home. At this visit, which is part of routine care, all women receive an educational intervention on contraception, which includes Jadelle® and the risks/side effects, benefits, and alternatives to the immediate postpartum implant.

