continuation, satisfaction, and pregnancy rates. They will have the option to leave the study at any point without any repercussions for their clinical care. We will have these questionnaires performed in a private location, in a one-on-one setting to increase comfort with discussing these issues, and patients will also be able to complete the questionnaire privately if they are literate and do not need assistance.

The primary foreseeable risk of all parts of the study is a breach of privacy and/or confidentiality. Study data will be stored securely in REDCap, which is HIPAA compliant and controls access on a study-by-study basis through the use of unique usernames and passwords. REDCap allows data fields to be flagged as identifiers, and investigators will utilize this feature to remove identifiers from datasets, which are exported for analysis.

Utilization of postpartum contraceptives, including placement of the implant how contraceptive use affects short interval pregnancy rates are the specific aims of this study; the study cannot be performed without offering contraceptives, including device placement. Fortunately, these medications are already in use in the study population and are non-experimental methods. Therefore, with proper counseling and informed consent, we believe the risks of the procedure will be acceptable to the patients and their partners.

Analysis Plan:

Methods & Models: The primary outcome of this study is contraceptive uptake rates in the intervention group. This study, with 200 women enrolled (100 from intervention clusters and 100 from control clusters) will be powered to detect a change in Jadelle uptake rates from 3% to 15% at 85% power and 5% significance, with an intra class correlation of 2%.

The satisfaction surveys will be administered at the six and twelve month well-child visits and will primarily assess patient experience with the medications, including side effects, continuation rates, and pregnancy rates. This quantitative analysis will provide direct feedback in terms of real-world use of contraceptives, their success rates, and their acceptability to the patients, which will also provide baseline research for future interventions to address issues surrounding patient choice of and satisfaction with different method of contraception, including the implant.

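### The primary uptake measure is ambiguous between any contraceptive and Jadelle, and the only power calculation is for Jadelle

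*Combined protocol and SAP*

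**What the plan says.** Under Analysis Plan, Methods & Models, the plan states: "The primary outcome of this study is contraceptive uptake rates in the intervention group". The sentence that follows describes 200 women, 100 per arm, as "powered to detect a change in Jadelle uptake rates from 3% to 15" percent, at 85% power, 5% significance and an intraclass correlation of 2%. The same statement appears under Phase 1, with software output for 3% against 15% and 100 per group that ends "Alpha= 0.050, Tails= 2, Power = 0.848". There is no other power calculation.

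Text pointing to any method:
- Study Title: a "home-based intervention to increase uptake of postpartum contraceptives".
- Hypothesis 1: "Offering routinely available contraceptives in a home setting can increase incidence of contraceptive initiation".
- Objective 1: "Increase uptake of routinely offered contraceptives in the postpartum setting".

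Text giving Jadelle prominence:
- Summary: a "home-based intervention to increase uptake of contraception, especially the contraceptive implant, Jadelle".
- Significance and Use of Results: whether home provision "can increase uptake, especially of the postpartum implant Jadelle® in the population of interest".
- Phase 1: the intervention is described with Jadelle first among the methods offered, and its low current use (about 4%) is explained by past difficulty of access.

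Visit 1 says that nurses bring pills, condoms, Jadelle and depot medroxyprogesterone acetate to intervention homes. Control women obtain methods from the CHD pharmacy or a clinic. IUDs are offered in both arms but placed at a clinic. No period is given within which a woman's uptake counts.

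**The concern.** Any-method uptake and Jadelle uptake are different endpoints. A woman who starts injections is a success on the first and a failure on the second. If home provision mainly moves women from pills or injections to the implant, Jadelle uptake can rise while overall uptake stays the same.

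While the plan leaves the choice open, either comparison could be presented as primary once the data are seen. A reader of a result on overall uptake would also have no planned control rate, target or power to set it against.

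Two smaller gaps lie in the same sentence. It names the intervention group only and no comparison. It also gives no period, although intervention women are offered methods at the visit and control women have to go elsewhere. A short period would count control women who obtain a method later as non-users.

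**Working it through.** **1. What the stated power belongs to.** Inputs from the Phase 1 output: p1 = 0.03, p2 = 0.15, n = 100 per arm, two-sided 5%, normal approximation. The formula is power = Φ[(d − 1.96·SE0)/SE1], where d = p2 − p1, SE0 uses the mean proportion and SE1 uses the separate proportions.

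- d = 0.12; mean p = 0.09
- SE0 = √(2 × 0.09 × 0.91/100) = 0.0405
- SE1 = √((0.03 × 0.97 + 0.15 × 0.85)/100) = 0.0396
- (0.12 − 1.96 × 0.0405)/0.0396 ≈ 1.03, so power = 0.848

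This reproduces the plan's figure. It is a Jadelle calculation, made as if women were individually randomised.

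**2. What exists for any-method uptake.**

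| Input | Jadelle uptake | Any-method uptake |
|---|---|---|
| Control rate | 3% (about 4% in the background text) | none |
| Target rate | 15% | none |
| Intraclass correlation | 2% | none |
| Power | 0.848, given as 85% | none |

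Power for any-method uptake cannot be derived from the documents.

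**3. The figure needed if Jadelle is primary.** The plan states an intraclass correlation of 2%, and the Timeline gives three clusters per arm. Equal cluster sizes are assumed.

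- Women per cluster: 100/3 = 33.3
- Design effect: 1 + (33.3 − 1) × 0.02 = 1.647
- Effective n per arm: 100/1.647 = 60.7
- SE0 = √(2 × 0.09 × 0.91/60.7) = 0.0519; SE1 = √(0.1566/60.7) = 0.0508
- (0.12 − 1.96 × 0.0519)/0.0508 ≈ 0.36, so power = 0.640
- With a t reference on 6 − 2 = 4 df: noncentrality 0.12/0.0508 = 2.36, power = 0.438

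The missing design effect is a separate issue. It is used here only so that a restated Jadelle figure is right.

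**4. Whether assumed rates settle the any-method question.** These are illustrations with 100 per arm, by the formula in step 1. The clustered column borrows the 2% intraclass correlation that the plan states for Jadelle.

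| Assumed gain | Assumed control rates | Unclustered power | Clustered power |
|---|---|---|---|
| 12 points | 10–80% | 0.40–0.69 | 0.26–0.48 |
| 25 points | 10–70% | 0.95–0.998 | 0.79–0.96 |

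The answer runs from poor to ample depending on a gain and a control rate that no document supplies. The illustration shows that the inputs are needed; it does not show a shortfall.

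**The case against.** The strongest defence is that Jadelle uptake was meant all along. The Jadelle effect size follows the primary-outcome sentence directly and can be read as making it operational. Phase 1, which is said to fulfil the first aim, is motivated by low Jadelle use, and two sections single the implant out. A trial may also hold a broad objective and test it through a narrower, powered measure. This stands as a fair reading, and it is why the point is one of ambiguity. It does not settle the matter: no section names Jadelle uptake as primary, and the title, Hypothesis 1 and Objective 1 are not limited to the implant. The text before the hypotheses even speaks of all contraceptives with abstinence included, which leaves the definition wider still.

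A reader might infer that the plan wrongly claims 85% power for contraceptive uptake in general. It does not: both power statements attach the figure to Jadelle. A reader might also infer that the trial is too small for any-method uptake. The documents do not support that, because it rests wholly on assumed rates and gains.

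It can fairly be added that the risk of choosing the outcome after the event is limited in part, since the Jadelle comparison and its target are already written down. That lessens the risk, but any-method uptake could still be put forward as the primary result.

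**Conclusion.** The point holds as an ambiguity in the primary outcome. The plan does not say which methods count, and the two readings lead to different endpoints. Under the any-method reading, the primary outcome has no stated control rate, target or power, and its power cannot be worked out from the documents; adequacy of the sample size for it is simply unknown. Under the Jadelle reading, the target is stated but the power is about 64% rather than 85%, given the plan's 2% intraclass correlation and three equal clusters per arm. It is about 44% if the analysis is a cluster-level t test on 4 df, which the Analysis Plan does not specify. The finding rests on the text alone; only the 64% and 44% depend on the cluster-size and test assumptions.

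**What to change.** In Methods & Models, replace the primary-outcome sentence with one that names a single measure. For example: *The primary outcome is uptake of [any routinely offered method, listed / Jadelle] within [period] of the postpartum visit, compared between intervention and control clusters.* The period should be the same in both arms and allow for the time control women need to reach a pharmacy or clinic. Make the other measure secondary.

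- **If Jadelle is primary:** keep 3% against 15%, and restate the power under the 2% intraclass correlation and six clusters (about 64%, or about 44% with a cluster-level t test on 4 df). Hypothesis 1 and Objective 1 may stay broad.
- **If any-method uptake is primary:** list the methods that count, including whether IUDs and abstinence do. State the assumed control rate, target rate and intraclass correlation with the resulting power, and say that the 85% does not apply to this outcome.

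The cost is a sentence and one power figure. One measure becomes secondary, and the stated power becomes less favourable for Jadelle, or rests on rates the sponsor must justify for any-method uptake. No visit or study procedure changes.

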Objective 2: Determine short-interval pregnancy, satisfaction, and continuation rates among women who received contraceptives in the home versus those that sought postpartum contraceptives through routine care.

Objective 3: Determine short-interval pregnancy, satisfaction, and continuation rates among women who opted for long-acting versus short-acting reversible contraceptives that were provided in the home setting.

Objective 4: Document side effects and adverse events occurring in the study population.

Methodology:

Study Design: This study is a cluster randomized trial of an intervention to increase uptake of postpartum contraception by providing them to women in their home and observe the effect on uptake in the community of interest. We have eight communities involved the healthcare services provides by the CHD that will be combined into six clusters, for study purposes. The clusters are independent of one another, except that some nurses offering the contraceptives may cover more than one cluster. Patients may also move between clusters over the course of the trial. Women will be recruited for enrollment into the CHD, and subsequently the study, blind to whether their cluster will be offered home-based contraception in the postpartum setting.

Operational Definitions/Proposed Intervention: This is a prospective community cluster-randomized study of a home-based intervention to increase uptake of postpartum contraceptives and study the direct effect on short-interval pregnancy, continuation, and satisfaction rates. The study has two phases.

Phase 1: The first phase fulfills AIM 1 and will involve a cluster randomized trial of the intervention, which is to bring and offer Jadelle[®], among all other routine postpartum contraceptive options, to the women in their homes, compared to routine care. Currently, around 4% of the population opts for Jadelle[®], which is less than expected, likely due to the fact that previously, Jadelle[®] was only offered

at a clinic inconvenient to the study population that required significant time and travel costs. Recently, implant availability has increased in the region due to the work of a non-governmental organization, and the nurses within the CHD were trained on implant placement. Therefore, Jadelle®, which was previously offered as part of the standard of care but not routinely available, now is accessible.

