Visit 1: At the postpartum visit in their home, patients will be enrolled in the study and provide informed consent. Once they have agreed to participate in the study, they will be offered postpartum contraception in the home in the intervention group, and through routine care (at CHD pharmacy or clinic location) in the control group. The nurses will bring all routinely available medications to the patient's home for those in the intervention clusters, including pills, condoms, Jadelle®, and depot medroxyprogesterone acetate. Patients who are breastfeeding will not be offered estrogen-containing methods. Participants in both the intervention group and control group will also be offered IUD placement; regardless of group, they will need to present to an area clinic setting for placement should they choose this method. Women opting for Jadelle® will receive immediate implant placement, and women that opt for other methods will receive their method of choice. 99% of patients in the community service program are seen for this postpartum visit, which is part of the standard of care for patients in this region.

Ninos Sanos Visits: The follow-up visits will occur through routine care as part of the Ninos Sanos program, into which all patients in the Madres Sanas program are automatically enrolled. Mothers are seen with their infants monthly in their home, including visits at six and twelve months after delivery. At these routine visits, the mothers enrolled in the study, in both groups, will complete a survey. The surveys will assess patient continuation rates and satisfaction with the contraceptive method of choice. Patients will also be queried about side effects such as: irregular bleeding, weight gain, headaches, rash, chest pain, moodiness, insertion site pain, cramps, acne, nausea, hair loss, or issues with breastfeeding after device placement. All patients will be questioned regarding repeat

pregnancy at these visits, as well, including outcomes of repeat pregnancies such as delivery, termination of pregnancy, or spontaneous abortion. We anticipate that this survey will take about 10 – 20 mins to administer. Additionally, the study nurses will perform a survey of their comfort and satisfaction with administering contraception in the home, which will be performed after enrollment is complete. These questionnaires are included with the submission.

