Programs Used: The analysis plan for this will use summary statistics to describe the patient population as well as the outcomes. We will use Student t (normally distributed variables) or non-parametric medians (non-normally distributed variables) tests for continuous data and χ^2 or Fisher's exact tests (for variables with cell sizes <5) for categorical data. Bivariate analyses will be performed to compare the groups. Variables that are significant ($P < 0.05$) in the bivariate analyses will be included in a logistic regression to determine independent predictors of repeat pregnancy. SPSS statistical software (version 24.0.0; IBM SPSS Inc, Chicago, IL) will be used for all the analyses.

References:

2. Guttmacher Institute. Sexual and reproductive health of young women in Guatemala. Online 2014, accessed 1/17/17 (<https://www.guttmacher.org/sites/default/files/factsheet/fb-dd-guatemala.pdf>)
4. LARCs: IUD and Implant Options. Planned Parenthood. Accessed 1/23/17 (<https://www.plannedparenthood.org/planned-parenthood-mar-monte/patient-resources/long-acting-reversible-contraception/larc>)

Timeline: After we have obtained IRAC/COMIRB APPROVAL and Francisco Marroquin University Ethics approval to proceed with the study, we will begin the study. We anticipate the first step of the trial to start January 2018. We expect this to be a 24-month study; the timeline will appear as follows:

Months	Activities
Dec 2017	Training, Jadelle placement refresher course

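### Six clusters are randomised 3 v 3, but every named test treats women as independent: false-positive rate about 11–14% for outcomes at 9–50%, and near 5% for Jadelle uptake only because Fisher's test is conservative

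*Combined protocol and SAP*

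**What the plan says.** Study Design states: "This study is a cluster randomized trial of an intervention to increase uptake of postpartum contraception". Eight communities are merged into six clusters, and the Timeline puts three in each arm. Phase 1, and Methods & Models under Analysis Plan, give 100 women per arm, a Jadelle uptake comparison of 3% v 15%, and an ICC of 2%. The power printout reads "Alpha= 0.050, Tails= 2, Power = 0.848".

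Tests are named only under Programs Used: Student t or median tests for continuous variables, chi-square or Fisher for categorical ones ("tests (for variables with cell sizes <5) for categorical data. Bivariate analyses will be performed to compare the groups"), then a logistic regression for repeat pregnancy. No section mentions a cluster-level summary, random effect, GEE, robust variance or small-sample correction. The word *groups* is not defined.

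On outcomes, Methods & Models makes contraceptive uptake primary without saying whether that means Jadelle or any method. Ninos Sanos Visits says "The surveys will assess patient continuation rates and satisfaction with the contraceptive method of choice", and that "All patients will be questioned regarding repeat" pregnancy. Objective 2 compares outcomes "among women who received contraceptives in the home versus those that sought postpartum contraceptives through routine care", which is worded by receipt and need not match the randomised arms.

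**The concern.** Women in one cluster share a community and nurses, so their outcomes are correlated; the plan accepts this by stating an ICC. A test that counts 200 independent women then understates the variance of the arm difference. Its confidence intervals are too narrow and its p-values too small.

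The undefined word *groups* does not rescue the plan. If it means the arms, the named tests are wrong for the design. If it means women with and without a repeat pregnancy, the arm comparison has no test at all. On either reading no analysis allows for cluster.

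At stake are the arm comparisons under Objectives 1 and 2, including the primary outcome if uptake means any method. Objective 3 (long- v short-acting methods) is not a randomised comparison and is outside this point.

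**Working it through.** **Inputs from the documents:** 3 clusters and 100 women per arm; ICC 0.02; two-sided alpha 0.05; Jadelle uptake 3% v 15% (current uptake about 4%); Fisher when a cell is below 5, otherwise chi-square.

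**Assumptions:** clusters of 33, 33 and 34 per arm; the ICC applied to outcomes other than Jadelle; outcome rates of 9–50%, since none is given for this population; chi-square without continuity correction; the Fisher rule read as observed cells.

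**1. The plan's own figure.** With mean rate 0.09:
- √(2×0.09×0.91) = 0.4047 and √(0.03×0.97 + 0.15×0.85) = √0.1566 = 0.3957.
- Power = Φ[(0.12×√100 − 1.96×0.4047)/0.3957] = Φ(1.028) = 0.848.

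The printed figure is reproduced with no clustering.

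**2. Size of the inflation.**
- Design effect = 1 + (33.3 − 1)×0.02 = 1.647.
- Approximate type I error of an unadjusted test = 2×[1 − Φ(1.96/√1.647)] = 12.7%.

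**3. Type I error of the named rule.** Beta-binomial clusters, same true rate in both arms, summed exactly over all 2×2 tables:

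| True rate | No clustering | ICC 0.02 |
|---|---|---|
| 3% | 1.1% | 4.5% |
| 4% | 1.7% | 5.9% |
| 9% | 4.3% | 11.1% |
| 15% | 5.1% | 12.8% |
| 30% | 5.1% | 12.8% |
| 50% | 5.6% | 13.7% |

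Rates above 50% mirror those below.

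**4. Sensitivity** (ICC 0.02 unless stated):
- *ICC 0.01:* about 3–4% at rates of 3–4%, and 8–10% at 9–50%.
- *ICC 0.05:* about 10–13% and 20–24%.
- *Continuity-corrected chi-square:* about 8–11% at 9–50%.
- *Fisher chosen on expected counts:* 5.1% at a 3% rate, 7.3% at 4%, 12.7% at 9%.
- *Uneven clusters (50/25/25):* about 5–7% at 3–4%, and 12–15% at 9–50%.
- *Method users only* (the natural denominator for continuation and satisfaction): with an assumed 50 per arm, about 4%, 6%, 9% and 10% at rates of 9%, 15%, 30% and 50%; with 80 per arm, about 8% at 9% and 11% at 15–50%.
- *Repeat pregnancy, all women:* Background cites a North American cohort that "found a 2.6% pregnancy rate one year post-placement, compared to an 18.6% pregnancy rate among the control group". Using those rates only as a range gives 3.8% at 2.6% and 12.9% at 18.6%; an assumed 5% gives 7.2%.

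**5. A test that respects the design.** A t test on the six cluster proportions (4 df) has simulated type I error of 3.7% at a 3% rate, 4.1% at 4%, 4.7% at 9%, 4.9% at 15% and 5.1% at 50%.

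**6. Its power for 3% v 15%.**
- Noncentrality = 0.12/√(0.1566×1.647/100) = 2.36; critical value 2.776 on 4 df; power 43.8% (about 45% by simulation).
- The formula of step 1 with 100/1.647 = 60.7 effective women per arm gives 64.0%.

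**The case against.** The strongest reply is that, at the only inputs the documents supply (Jadelle at 3–4%, ICC 0.02), the error is 4.5–5.9%, close to nominal. The 11–14% needs assumed rates, a borrowed ICC, equal clusters and uncorrected chi-square. That is a fair limit on the size, and the sensitivity results show it. It does not remove the defect. The Jadelle figure is near 5% because Fisher's conservatism happens to offset a rise of 3.5 to 4 times from clustering. Under the other variants tried, the error at 9–50% with all 100 women per arm stays above nominal.

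A second reply is that the alternatives are not equally safe with six clusters. A GEE with bias-reduced variance gave simulated type I error of 8.7–9.7% at a 4% rate, worse than the rule criticised here; with 4 df it gave 1.8% and 3.3% at rates of 15% and 50%. The excess at 4% appears to come from the roughly 9% of null trials in which an arm has no events. Leaving those trials out brought the 4-df version to 0.2%. This stands as a caution and favours the cluster-level t test. The feasibility of a cluster-adjusted repeat-pregnancy regression with six clusters was not checked.

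Third, Study Design says nurses may cover more than one cluster and women may move between clusters. The calculations treat clusters as independent, so the error rate of the proposed test is less assured than step 5 suggests.

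**Conclusion.** The concern holds and must be fixed before the data are seen. That no analysis allows for cluster is certain from the text. The size is conditional. With equal clusters, ICC 0.02, uncorrected chi-square and all 100 women per arm, an arm comparison at nominal 5% has true error of about 11–14% at outcome rates of 9–50%, and about 4.5–6% for Jadelle uptake at 3–4%. Inflation is smaller when only method users are counted. For repeat pregnancy no single value can be given, because the documents state no rate for this population. Whether the primary outcome falls in the inflated range depends on whether uptake means Jadelle or any method.

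**What to change.** - State that the groups for Objectives 1 and 2 are the randomised arms. Say for each outcome whether the denominator is all enrolled women or method users.
- Name one primary analysis that accounts for cluster. The simplest that was checked is a t test on the six cluster proportions or means (4 df), reporting the difference with its 95% CI. A mixed model or GEE with a small-sample correction is possible, but should specify how an arm with no events is handled. An exact permutation test is not usable: with 20 possible allocations its smallest two-sided p is 2/20 = 0.10.
- Keep the unadjusted tests for description only.
- In the repeat-pregnancy regression, use a random effect or a small-sample-corrected GEE. Do not use fixed cluster terms: each cluster lies wholly in one arm, so intercept, arm and five cluster indicators are 7 columns of rank 6, and the arm effect cannot be estimated.
- Restate power for the analysis chosen.

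The wording costs little; the power cost is large and comes from having six clusters. For 3% v 15% at ICC 0.02 the 4-df test has about 44% power, against the stated 85% (about 52% at an assumed ICC of 0.01, 30% at 0.05). Enrolling all 260 expected eligible women gives about 49%. With three clusters per arm, power cannot exceed about 79% at ICC 0.02 however many women join: the noncentrality tends to 0.12/√(0.02×0.1566/3) = 3.71. A restated target may therefore need more clusters.
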